laboratory values on the relevant page of the electronic CRF and will assess the etiology of the clinically relevant abnormal laboratory values.

Clinically relevant abnormal laboratory values are only documented on the AE form of the electronic CRF, if the patient is discontinued, hospitalized, or, in the investigator's opinion, it should be considered as an AE.

Abnormal laboratory results caused by ulcerative colitis should not be reported on the AE form.

Pregnancy

Pregnancy tests will be performed at the screening visit, week 0, week 4 (in case of early cross over), week 6, week 10, and week 12 of the study. Women of child bearing potential will be asked about contraception compliance at each study contact. If there is concern for pregnancy during the study, the subject will be asked to immediately come to the site for a pregnancy test. The PI (sponsor-investigator) will report to Novo Nordisk any pregnancy occurring during the trial period. Reporting of pregnancy by sponsor-investigator should occur within the same timelines described above for reporting of serious adverse events.

WITHDRAWAL OR STOP OF STUDY DRUG CRITERIA

CRITERIA IN INDIVIDUAL CASES

Any patient can withdraw from the study at any time without personal disadvantages and without having to give a reason. The time of withdrawal, the results available up to that time, and, if known, the reason for withdrawal must be documented in the CRF. The investigator can also discontinue the study after considering the risk-to-benefit ratio, if he/she no longer considers the further participation of the patient justifiable. The date of and the primary reason for the withdrawal as well as the observations available at the time of withdrawal are to be documented on the electronic CRF.

Reasons leading to the **withdrawal** of a patient can include the following (primary reason must be determined):

- inclusion criterion not fulfilled, or exclusion criterion fulfilled; coming to knowledge after recruitment
- patient's request
- technical/logistical reasons (e.g. a change in place of residence, not referred by family physician, etc.)
- withdrawals due to adverse events (including non-serious adverse events leading to withdrawal)
- withdrawal to known adverse drug reaction (ADR as listed above), which is defined as severe according to the listed severity criteria (event/symptom prevents normal daily activities).
- Acute gallstone disease confirmed by
 - o Signs and symptoms of acute gallstone disease

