Standard Operating Procedures exist for users of the DMC. Only authorized persons are authorized for data entry and access. Data security systems require password protected identification codes for data entry and provide protection against data manipulation. The database is located on a server protected by firewalls. Access to the database server will not be allowed by users on computers outside of the firewall-protected zone. Virus protection software is installed on each study machine. System access to computer systems will be audited. Redundant backups and off-site backup storage will allow for quick restoration of data in the unlikely event that a hardware failure, disaster, or security breach should occur. Servers and backups will be located in a secured location with access limited to authorized personnel.

Data cleaning will include range and edit checks, cross form edit checks, query generating and tracking and periodic data status reports. Any data errors or inconsistencies detected after data entry will be automatically tracked, communicated and resolved using a web-based application. An audit trail of all data changes over the life of the study will be maintained. All study raw data, forms, documents, software programs, software applications and computer data files will be indexed and archived routinely. Strict version control of documents and software applications will be instituted. Retention of study documentation after study completion will conform to FDA and NIH requirements.

Standardized study management reports will be generated monthly during the recruitment phase of the study. These reports will be used to track study progress including patient enrollment, randomization, compliance, patient status changes, and study events.

DATA ANALYSIS

Efficacy analyses will primarily be based on a modified intent-to-treat {mITT} analysis set, which includes all randomized patients, who took at least one dose of the investigational product. Statistical tests will be 2-sided and performed at the 0.05 level of significance. Missing data will be imputed for the mITT population using the last observation carried forward (LOCF) method. Baseline observations will not be carried forward if all subsequent measurements are missing.

Primary analyses

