The primary outcome is the reduction of the mean 7-day bowel frequency of 30% compared to baseline (baseline is defined as the mean 7-day bowel frequency in a 7-day period during the screening period before week 0). A crossover trial will be performed. Subjects with a history of averaging > 8 bowel movements per day over a 7-day span will be entered into the study and the

order in which they receive treatments (liraglutide or placebo) will be randomized. At the end of each week, the average number of bowel movements the subject had during that week will be computed. A repeated measure mixed model will be fit to the data with treatment (liraglutide or placebo), period and treatment sequence as fixed effects and the repeated measures within subject as a random effect. After the model is run, any non-significant effects for period or treatment sequence will be removed from the model. The treatment effect will remain in the model and is the outcome of interest. P-value less than 0.05 will be considered statistically significant. In a sensitivity analysis the same model will be run without removing any effects. P-value less than 0.05 will be considered statistically significant.

Secondary analyses

Continuous secondary outcomes (stool frequency, clinical PDAI) will be summarized using descriptive statistics (mean, median, standard deviation, minimum, and maximum) of the values at each assessment and the change from baseline to each assessment. A repeated measure mixed model will be fit to the data with treatment (liraglutide or placebo), period and treatment sequence as fixed effects and the repeated measures within subject as a random effect. After the model is run, any non-significant effects for period or treatment sequence will be removed from the model. The treatment effect will remain in the model and is the outcome of interest. P-value less than 0.05 will be considered statistically significant.

Safety analyses

The safety analyses will comprise all included patients, who got at least one dose of the investigational product.

- Number of study patients, who discontinued therapy
- Adverse events grouped by body system
- Changes in laboratory values

Exploratory analyses

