We will perform exploratory analyses using descriptive statistics (mean, median, standard deviation, minimum, and maximum) and bivariate analyses of the values at each assessment and the change from baseline to each assessment. In the evaluation of the PROMIS measure for incontinence, PROMIS measures utilize a T-score metric where a score of 50 is the mean of a relevant reference population and 10 is the standard deviation. Additionally, a clinically minimally important difference is reflected by a change of 2.

Missing data

Due to short and intensive period of follow-up for the primary outcome, we do not anticipate significant missing data.

SAMPLE SIZE CALCULATION

The analysis will be based on the within-subject difference between two one-week averages of the number of bowel movements per day (BMPD). A one-sample t-test will be used to test the

null hypothesis that the mean difference is zero. With a sample size of 10 subjects and Type-I 0.05 (2-sided), the power is 0.80 against a difference of 1 standard deviation (SD) of the difference (not SD of the individual outcomes). The first average within each patient, by design, will be greater than 8 BMPD, and the range is most likely to be 8-11. The standard deviation (SD) of such an outcome can't (mathematically) exceed 1.5, and this will be used in the sample size calculations as the SD of each weekly average (control and treatment). Additionally, the SD of the difference depends on the correlation between the two weekly averages. Taking that into account, the power is 0.80 against a difference of 2.1 BMPD if the correlation is 0, 1.8 BMPD if the correlation is 0.25, 1.5 BMPD if the correlation is 0.50, 1.1 BMPD if the correlation is 0.75. Assuming a baseline average of 10 BMPD, the design has good power against relative changes of 21% or higher if the within-subject correlation is zero. The power increases with increasing positive correlation and, naturally, is higher against larger effects. If patients drop out during the study the power will decrease, however patents will be carefully selected and thus dropouts are unlikely to occur.

FUTURE PERSPECTIVE

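### LOCF has no limit at the crossover: read literally, a patient with no period 2 data has a period 1 value entered under the other treatment, which shrinks the contrast by about 10% per such patient if there is no period effect

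*Combined protocol and SAP*

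**What the plan says.** **The rule (Data Analysis, opening paragraph).** Efficacy rests mainly on the mITT set, "which includes all randomized patients, who took at least one dose of the investigational product". Then: "Missing data will be imputed for the mITT population using the last observation carried forward (LOCF) method". The single limit follows: "Baseline observations will not be carried forward if all subsequent measurements are missing".

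**Baseline (Primary analyses).** It is a 7-day mean taken during screening, before week 0. No separate period 2 baseline is defined.

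**The model (Primary analyses).** A mixed model is fitted to weekly means "with treatment (liraglutide or placebo), period and treatment sequence as fixed effects and the repeated measures within subject as a random effect". Period and sequence are then dropped if not significant. The only sensitivity analysis is: "In a sensitivity analysis the same model will be run without removing any effects".

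**Expected losses.** The Missing data paragraph says: "Due to short and intensive period of follow-up for the primary outcome, we do not anticipate significant missing data". Sample Size Calculation says "thus dropouts are unlikely to occur", and the Recruitment Plan expects every randomized patient to complete. No rate is given.

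**How a patient could leave.** The withdrawal criteria include "withdrawals due to adverse events (including non-serious adverse events leading to withdrawal") and severe forms of the listed drug reactions. A final examination follows, and patients withdrawn after the first dose are not replaced.

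**The concern.** In a crossover the treatment effect is the difference between a patient's two periods. If period 2 is empty and LOCF fills it from period 1, a liraglutide value is entered as a placebo value, or the reverse. That patient then contributes a difference of about zero, whatever the drug did. The baseline limit does not prevent this, because the value carried is an on-treatment period 1 value and not the screening week.

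The planned sensitivity analysis would not reveal it. It refits the same model, and nothing says it uses other than the same imputed data.

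At stake is the effect estimate more than the p-value. The trial has 10 patients, and the third study aim is to collect first efficacy data for planning a larger study.

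**Working it through.** **Inputs.** From Study Design, Data Analysis and Sample Size Calculation: 10 patients, 1:1 to two sequences (5 + 5 if balanced), two-sided 0.05, SD of each weekly average 1.5. Assumed, because the plan gives no value: the number *k* of patients with no period 2 data (1, 2 or 3), and the period effect.

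**1. The plan's own figures.** One-sample t-test, 9 df, noncentrality √10 × 1 = 3.16: power 0.803, against 0.80 stated. Power of 0.80 needs 0.996 SD of the difference. Detectable difference = 0.996 × 1.5 × √(2(1 − ρ)):

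| ρ | computed | stated |
|---|---|---|
| 0 | 2.11 | 2.1 |
| 0.25 | 1.83 | 1.8 |
| 0.50 | 1.49 | 1.5 |
| 0.75 | 1.06 | 1.1 |

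All reproduce. Below, ρ = 0.5, so the SD of the difference is 1.5 × √(2 × 0.5) = 1.5, and the complete-data standard error is 1.5/√10 = 0.47.

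**2. Expected estimate under literal LOCF, one value per period.** Let *D* be the true reduction (placebo minus liraglutide), *P* the period effect (period 2 minus period 1), and *a* and *b* the leavers in the liraglutide-first and placebo-first sequences, with *k* = *a* + *b*. Remaining differences have mean *D* + *P* (liraglutide-first) or *D* − *P* (placebo-first). Leavers contribute 0.

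Expected estimate = [(5 − *a*)(*D* + *P*) + (5 − *b*)(*D* − *P*)]/10 = *D*(10 − *k*)/10 + *P*(*b* − *a*)/10.

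**3. No period effect (*P* = 0), *D* = 1.5.** 200,000 simulated trials per cell, one-sample t-test:

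| k | LOCF estimate | 95% CI coverage | power, LOCF | power, complete pairs |
|---|---|---|---|---|
| 1 | 1.5 × 0.9 = 1.35 | 0.95 | 0.74 | 0.75 |
| 2 | 1.5 × 0.8 = 1.20 | 0.91 | 0.67 | 0.68 |
| 3 | 1.5 × 0.7 = 1.05 | 0.85 | 0.57 | 0.60 |

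Type I error stays at or just below 0.05. The damage is to the estimate and its interval; the extra loss of power is small.

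**4. Weekly mixed model, no period effect.** With an immediate effect and two leavers, LOCF gave 1.20 and observed data 1.45 for a true 1.5. A separate run with four weekly values per period and a true 2.1 gave about 1.9 (one leaver) and 1.7 (two) with LOCF, against 2.05 to 2.14 without imputation.

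If the effect instead follows the dose steps (assumed 1/3, 2/3, then full, with a full effect of 1.8 and so a 6-week average of 1.5), take a liraglutide-first patient who leaves after week 4. Period 1 averages 5/6 of the full effect and the carried period 2 shows all of it, so that patient contributes −1.8/6 = −0.3. One leaver gives (9 × 1.5 − 0.3)/10 = 1.32, two give (12 − 0.6)/10 = 1.14.

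**5. With a period effect.** For two liraglutide-first leavers and *D* = 1.5 the formula gives 1.2 − 0.2*P*: 1.60, 1.40, 1.00 and 0.80 for *P* = −2, −1, +1, +2. Type I error (*D* = 0, period kept, 8 df), all leavers liraglutide-first:

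| size of *P* | 1 leaver | 2 | 3 |
|---|---|---|---|
| 0.5 | 0.050 | 0.055 | 0.071 |
| 1 | 0.050 | 0.071 | 0.114 |
| 2 | 0.05 | 0.10 | 0.22 |

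With one leaver in each sequence it is not raised (0.03 and 0.01 for *P* of 1 and 2).

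**The case against.** **It may be only an omission.** The plan nowhere says that period 1 values are to fill period 2, and the ban on carrying baseline forward suggests no wish to pass off one condition's value as another's. A careful analyst might stop at the crossover. That stands as a guess at intent. But the sentence covers all missing mITT data, and two analysts could follow it to different primary results.

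**The trigger may never occur.** The plan expects no dropout. The study drug section allows a step back in dose for intolerance. The section on expected reactions reports no severe cases of the commoner ones in comparable patients. Early crossover at week 4 moves non-responders into period 2 instead of losing them. All of this stands, and one leaver's shift of 0.15 is small against 0.47.

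**Not every loss counts.** A patient who leaves in period 2 after at least one weekly mean, or who crosses over or stops early for non-response, has gaps filled from the same treatment. Patient request appears both as a reason for withdrawal and as a reason to stop drug with continued follow-up, so it is not a clear route.

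**A reader might infer that the trial's type I error is inflated.** The documents do not support that. It needs two or more leavers concentrated in one sequence and a sizeable period effect, for which no value is given. One-sided loss is plausible for drug reactions, since patients lost before period 2 would mainly be liraglutide-first, but this is inference.

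**Conclusion.** The gap in the rule is certain; the harm is conditional. As written, LOCF gives a wrong contrast whenever a patient has no period 2 data. With no period effect, and if leavers would have had the same average effect as the others, the estimate shrinks by about 10% per such patient. Two or three of ten leave it 20 to 30% low, with interval coverage near 0.91 or 0.85 (one value per period, SD of the difference 1.5). With a period effect and unequal losses it can move either way.

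A reader might also infer that fitting the model to observed data secures its error rates. It does not. In a weekly random-intercept check with an assumed patient-by-period SD of 0.75, type I error was about 0.4 with full, observed or LOCF data alike. Those rates depend on the covariance structure and degrees of freedom, which is a separate matter. What the fix removes is the cross-period bias in the estimate.

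It should be fixed, because each patient is a tenth of the sample and the change is one of wording. No change to the sample size follows.

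**What to change.** For the mixed-model analyses, replace the LOCF sentence with: *No value is carried from one period to the other; the mixed model is fitted by REML to all observed weekly means of mITT patients, without imputation.*

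At minimum, if LOCF is kept, add: *LOCF is applied only within the same period and treatment.*

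An analysis of patients with data in both periods is optional and supportive only. If the leavers are the liraglutide-first patients with the highest period 1 values, it reads high (1.61, 1.71, 1.81 for a true 1.5 with one, two or three leavers). Where losses are unequal, dropping a non-significant period term can bring some bias back, so read the result beside the planned run that keeps all effects.

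**Cost.** Wording only; visits, treatment and sample size are untouched. The interval widens somewhat (mean width 2.48 against 2.07 in the one-value-per-period setting with two liraglutide-first leavers), and the analysis assumes data are missing at random. There is no power gain.

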- 2. To study safety, tolerability and quality of life in the trial period of liraglutide vs placebo application
- 3. To collect first data about the efficacy of a liraglutide therapy in patients with an ileo-anal pouch anastomosis (IPAA) and abnormal high bowel frequency in the absence of inflammation for planning a larger phase 3 study in this orphan status patient population

STUDY DESIGN

Randomized, double-blind, 2-period, placebo- controlled, crossover proof of concept study. Ten patients with increased bowel frequency is defined as > 8 bowel daily/week without significant pouchitis* will be randomized to either liraglutide or placebo treatment for 6 weeks (Period 1). Subjects will be randomized 1:1 to 1 of 2 treatment sequences, liraglutide-placebo or placebo-liraglutide, and receive either liraglutide or volume-matched placebo. After a washout period of at least 5 days (the half-life of liraglutide is 11-12 hours, thus the minimal washout period of 5 days is equal to 10 half-life's) patients will be crossed over to the other treatment arm (Period 2). Since high bowel frequency can result in significant malaise and dehydration, patients not responding to the respective therapies in period 1 may be crossed over after 4 weeks of therapy or in period 2 can be terminated early at week 4. The rationale behind the early termination is based on 2 open label cohorts reporting the efficacy of liraglutide or exenatide in patients with high output ileostomies (the patient group the most comparable to the pouch patient population). GLP-1 receptor agonist therapy even at the lowest dose showed an almost immediate effect reducing the ostomy output after 1-3 days in most patients.^{26, 27} Thus, patients not responding to a 4-week therapy with a GLP-1receptor agonist are highly unlikely to respond if the therapy would be continued.

[figure not shown]

Figure 3: Study design

Randomization: Subjects will be randomized 1:1 to 1 of 2 treatment sequences, liraglutide—placebo or placebo—liraglutide, and receive either liraglutide or volume-matched placebo.

STUDY DRUG, SUPPLY OF STUDY DRUG AND RECRUITMENT PLAN

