Liraglutide (Victoza®) or placebo will be supplied by Novo Nordisk A/S and dispensed by the UNC investigational pharmacy. The liraglutide or placebo solution for subcutaneous injection will be delivered as blinded pre-filled, multi-dose pens that deliver doses of 0.6 mg, 1.2 mg, or 1.8 mg (6 mg/mL, 3 mL cartridge). In order to blind the product, a clinic variant of the marketed product is supplied. The clinic variant of the 3 ml cartridge is produced with an army green closure cap compared to a light blue closure cap in the marketed Victoza® product. The push button and cartridge holder are light brown, while the marketed pen-injector has a light blue push button and cartridge holder. Neither closure cap nor the pen is in contact with the product and the differences in colors have no impact on the stability of the product. The investigator will ensure the availability of proper storage conditions, and record and evaluate the temperature. The dose escalation and administration of liraglutide therapy will be performed according to the current FDA approved prescribing information to improve glycemic control in adults with type 2 diabetes. A Directions for Use (DFU) for the device will be provided by Novo Nordisk A/S. It will be handed out to subject at first dispensing visit and the subject must be trained according to DFU. Liraglutide will be administered once daily independently of meal. The patient will choose the optimal administration time (morning, midday, evening) and will continue with this timing throughout the study. Liraglutide will be injected subcutaneously in the abdomen, thigh or upper arm according to the DFU. The patient will be instructed by the investigator how to use the pen using the DFU provided by Novo Nordisk A/S. Treatment will be initiated at 0.6 mg per day for one week. The patient will be instructed to increase the dose to 1.2/day and 1.8 mg/day in week 2 and in week 3, respectively. From week 3 after start of drug until week 6 (or week 8-12 in period 2 depending on randomization) the patient will apply 1.8 mg/day liraglutide. In case of intolerance (e.g. occurrence of refractory nausea) at a higher dose (e.g. 1.8 mg daily, the highest dose in this trial) liraglutide can be reduced to the previous level.

LIRAGLUTIDE AND TACHYPHYLAXIS

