So far extent of tachyphylaxis of the effects of liraglutide on gastric emptying are inconclusive or not well defined. Liraglutide (1·2 mg, 1·8 mg, or 3·0 mg daily) delays 1-h gastric emptying, as measured by the plasma acetaminophen method (which reflects predominantly the gastric emptying of liquids, not solids) compared with placebo.³¹⁻³⁴ However, tachyphylaxis of the delay of gastric emptying seems to occur over time but the extent is not clear. For liraglutide 3.0 mg daily one study reports complete tachyphylaxis for delay in gastric emptying based on the plasma acetaminophen method after 5 weeks whereas another study, using a scintigraphy method for gastric emptying which includes the emptying of solid food describes partial tachyphylaxis but still significant efficacy compared to placebo after 16 weeks of therapy.^{32, 34} All studies so far have been performed in patients with an intact GI-tract. The question remains if tachyphylaxis occur in patients with low GLP-1 levels and potentially upregulated GLP-1 receptors in the absence of

a colon. In the only available 2 studies analyzing the effects of liraglutide or exenatide on jejunostomy output no tachyphylaxis was reported after 8 weeks(liraglutide) or 1 year (exenatide) of therapy.^{26, 27}

RECRUITMENT PLAN

We estimate to screen 20 - 25 pouch patients/month and randomize 1 patient/month. We expect that all patients will complete the study after randomization. Under the direction of [name], the University of North Carolina has a Multidisciplinary Pouch Clinic that involves gastroenterology and surgery care for pouch-related disorders. We follow approximately 450 patients from throughout the southeast region of the United States that are treated regularly in our clinic.

STUDY MILESTONES

Months	1-4	4-16	16-22
Activities	Start-up of	Recruitment	Follow-up last
	trial		patients
	IRB		Analysis of
	IND/FDA		clinical data

INCLUSION AND EXCLUSION CRITERIA

INCLUSION CRITERIA

- Informed consent will be obtained before any trial-related procedures
- Age > 18 years
- Patients with IPAA and bowel frequency > 8 bowel movements in 24 hours on at least 4
 of 7 days/week and presence of high bowel frequency > 4 weeks despite adequate
 therapy for acute pouchitis or Crohn's like disease of the pouch

EXCLUSION CRITERIA

- Significant pouch inflammation defined as an endoscopic pouch disease activity index
 (PDAI) ≥ 4

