 New start of biologics, antibiotics, steroids, anti-motility therapies (e.g. hyoscyamine, loperamide, atropine)

• Non - steroidal anti-inflammatories (NSAIDs) as long-term treatment, defined as use for at least 4 days a week each month

STUDY OUTCOMES

PRIMARY OUTCOME

Reduction of the mean of the 7-daily bowel frequency by 30% in week 4 and week 10.

SECONDARY OUTCOME

- Safety and Tolerability of GLP-1
 - Number of study patients, who discontinued therapy
 - Adverse events grouped by body system
 - Changes in laboratory values
 - Changes in nausea, appetite, abdominal pain and well being
- Change in bowel frequency during day (patient is awake from morning until bedtime) and during night (patient is asleep and has to get up because he has a bowel movement) comparing screening period to week 1, week 2, week 3 and week 4 during active treatment with liraglutide or placebo in period 1 or in period 2 (week 7, 8, 9 and 10).
- Change in clinical PDAI week 0 and week 4 and week 10

EXPLORATORY OUTCOMES

- Change in stool calprotectin from baseline
- Change in SF-36
- Change in PROMIS measures
- Change in PROBE score
- Change in body weight and experience of nausea, decreased appetite or increased abdominal pain
- Change in PDAI at week 6 or week 12 in patients responding to liraglutide therapy
- Change in bowel frequency during day (patient is awake from morning until bedtime) and during night (patient is asleep and has to get up because he has a bowel movement) comparing screening period to week 5 and 6 in period 1 or 11 or week 11 and 12 in period 2.

ASSESSMENTS/INDICES

In regard to when the assessments are performed please also refer to study visits and table study visits and assessments.

- Patient diary (performed daily): Bowel frequency during the day (6 am-6 pm) and night (6 pm -6 am) and recording of bowel movement consistency (liquid, pasty or formed)¹⁴
- Patient diary (performed daily): Timing of bowel movement in relation to meals (within 15 min, 30 min or >30 min)
- Modified pouch disease activity index (mPDAI)³⁵

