Review of glucose diary and			Χ	X	Х	Х	Х	X	Х	Х		
hypoglycemic protocol and												
reporting form												
Assessment of response ^h					Χ				Х			
PROMIS questionnaires, SF36,	Х			Х	Х	Х		Х	Х	Х		
PROBE												
Study drug dispensation		Χ			X ⁱ	Χ						
Study drug collection										X^{j}		

^a Clinical PDAI excluding pouchoscopy

^bCBC, AST, ALT, AP, Bilirubin, Creatinine, CRP. Serum samples for GLP-1 baseline fasting if possible (Screening or week 0).

^c Subject diary will be maintained electronically and completed daily reporting stool frequency, rectal bleeding, fecal urgency or abdominal cramps, and/or fever. The patient will complete this diary each day, beginning with the screening visit and ending at the visit. The average 7-day bowel frequency will be calculated for each 7-day period. For the clinical PDAI scores the last three days of diary entries before each visit will be used to calculate stool frequency and fecal urgency/abdominal pain scores.

^d Phone visit only with review of diaries and dose increase of study drug if tolerated. Patient will mail stool sample calprotectin or bring in person.

^f Crossover occurs after at least 5 days of washout after the last study dose

^g Pregnancy test at week 4 in case of early crossover

h Assessment of response: If average weekly bowel frequency of patient did not decrease by at least 15% compared to baseline the patient can proceed to early crossover (Period 1 week 4) or early termination (Period 2 week 10).

Non-responder at Period 1 week 4 receive study drug for period 2 to start 5 days after the last study dose of period 1

^jCollection of study drug from non-responders in Period 2 week4 and all patients who were responding at Period 2 week 10 and completed study at Period 2 week 12.

^k For non-responders at Period 2 week 10 the safety outcomes below will be assessed at Period 2 week 12. For this patient group at Period 2 week 12 only adverse events (review adverse events diary) and concomitant medication will be assessed at Period 2 week 12. An alternative approach is a phone visit at Period 2 week 12 (similar to the final visit at Period 2 week 14) and patient returns all study medication from period 1 and 2 before Period 2 week 12.

REFERENCES

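### The primary model does not say which weeks enter it; fitted to every week with only a patient intercept, its test does not hold the 0.05 level and its estimate averages over dose escalation

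*Combined protocol and SAP*

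**What the plan says.** Three sections of the combined protocol and SAP describe the primary comparison.

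- STUDY OUTCOMES, Primary outcome: "Reduction of the mean of the 7-daily bowel frequency by 30% in week 4 and week 10". Day and night frequency in weeks 1-4 and 7-10 is secondary; in weeks 5-6 and 11-12 it is exploratory.
- SAMPLE SIZE CALCULATION: "The analysis will be based on the within-subject difference between two one-week averages of the number of bowel movements per day (BMPD"), tested with a one-sample t-test in 10 subjects.
- DATA ANALYSIS, Primary analyses: "At the end of each week, the average number of bowel movements the subject had during that week will be computed". A repeated measures mixed model is then fitted with treatment, "period and treatment sequence as fixed effects and the repeated measures within subject as a random effect". Non-significant period or sequence terms are removed; a sensitivity analysis keeps them.

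The last section does not state which weekly averages enter the model. It has no week term and no patient-by-period term, and it gives no residual covariance structure or degrees-of-freedom method. Weekly averages are needed for other purposes too: note c to the table of visits says "The average 7-day bowel frequency will be calculated for each 7-day period". Computing them therefore does not show that all of them enter the primary model.

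**The concern.** The sentence about every week's average comes directly before the model is introduced, so fitting all weeks is a natural reading. Two consequences would follow.

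- **Test.** Several weekly means from one patient in one period share whatever was particular to that patient in that period. A patient intercept does not capture this. The model would then treat four or six correlated values as independent evidence on the treatment contrast.
- **Estimate.** One pooled treatment effect averages over the escalation weeks ("The patient will be instructed to increase the dose to 1.2/day and 1.8 mg/day in week 2 and in week 3, respectively") and, with six weeks, over weeks 5-6. It equals the week 4/10 effect only if the effect is the same in every week. STUDY DESIGN gives some support for that, saying GLP-1 receptor agonist therapy "even at the lowest dose showed an almost immediate effect reducing the ostomy output after 1-3 days in most patients". The dose steps are a reason for doubt, as is the remark that "tachyphylaxis of the delay of gastric emptying seems to occur over time but the extent is not clear".

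Weeks 5-6 and 11-12 raise a further question. Patients without a 15% decrease can leave treatment at week 4 or week 10, and missing data are filled by LOCF. Nothing says whether those untreated weeks count as missing.

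The study has 10 patients and one primary p-value, so two analysts following the same text could report different estimates and different p-values.

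**Working it through.** **1. The plan's own power.** Inputs from SAMPLE SIZE CALCULATION: n = 10, two-sided 0.05, difference of 1 SD of the within-patient difference, weekly SD 1.5. The noncentral t with 9 df and noncentrality √10 gives 0.803 (stated 0.80). The SD of the difference is 1.5·√(2(1−r)), and 80% power needs 0.996 SD. For r = 0, 0.25, 0.50 and 0.75 the detectable differences are 2.11, 1.83, 1.49 and 1.06 BM/day (stated 2.1, 1.8, 1.5 and 1.1). The sample-size figures reproduce.

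**2. Only weeks 4 and 10 in the model.** There is one value per period, so within-period covariance does not arise. Simulated type I error is 0.046-0.053. With period and sequence kept, the test has 8 df and power at 1 SD is 0.791.

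**3. All weeks, patient intercept only: type I error.** The documents give no within-period correlation, so it is assumed and shown as a range. Take 5 patients per sequence, w weeks per period and within-patient variance 1. Split that variance into a patient-by-period share s and a weekly part 1−s.

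- Expected treatment mean square with no effect: (1−s) + w·s.
- The residual pools the patient-by-period line (8 df, same expectation) with the weekly line (20(w−1) df, expectation 1−s). Total df: 68 for w = 4, 108 for w = 6.
- s = 0.5, w = 4: treatment 0.5 + 2 = 2.5; residual (8×2.5 + 60×0.5)/68 = 0.735; ratio 3.40. The critical value 1.995 acts like 1.995/√3.40 = 1.08, a two-sided normal tail of about 0.28 (simulated 0.29).
- s = 0.5, w = 6: treatment 3.5; residual (8×3.5 + 100×0.5)/108 = 0.722; ratio 4.85; 1.982/√4.85 = 0.90, tail about 0.37 (simulated 0.37).

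A linear week trend common to both treatments goes into the residual, because there is no week term. For w = 4 and a 2 SD trend, the weekly values −1, −1/3, 1/3, 1 have sum of squares 2.22. Over 20 patient-periods that is 44.4, which adds 44.4/68 = 0.65 to the residual. At s = 0 the ratio falls to 1/1.65 = 0.60, and 1.995/√0.60 ≈ 2.57, tail 0.010 (simulated 0.012).

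Simulated type I error, 4 / 6 weeks per period:

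| Share s | No trend | Trend 2 SD |
|---|---|---|
| 0 | 0.05 / 0.05 | 0.012 / 0.016 |
| 0.1 | 0.09 / 0.12 | 0.03 / 0.05 |
| 0.3 | 0.19 / 0.26 | 0.08 / 0.15 |
| 0.5 | 0.29 / 0.37 | 0.14 / 0.24 |

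With AR(1) weekly errors at 0.5 and no trend, type I error is 0.18-0.22 for four weeks and 0.21-0.24 for six, depending on whether the correlation carries across the washout. Adding a week term removes the conservatism but not the inflation (s = 0.3, 2 SD trend: 0.19 / 0.26). Adding a patient-by-period effect as well restores 0.048-0.053.

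**4. LOCF.** Take six weeks, s = 0 and no trend, and fill weeks 5-6 in 25% to 100% of patient-periods. Type I error rises to 0.085-0.19 if these are chosen at random, and to 0.10-0.19 if the highest week-4 values are carried forward.

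**5. Estimate.** If the effect were proportional to the protocol's dose steps (0.6/1.8 = 1/3, 1.2/1.8 = 2/3, then 1), the pooled effect relative to week 4 is (1/3 + 2/3 + 1 + 1)/4 = 75% over four weeks and (1/3 + 2/3 + 4)/6 = 83% over six. If the effect is immediate and constant, it is 100%.

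**The case against.** The outcome and sample-size sections both point to one weekly average per period, and the other weeks appear under secondary and exploratory outcomes. Those items concern day and night counts, so they do not settle the primary model, but they make a six-week primary model the least supported reading. On the week 4/10 reading there is no inflation. The analysis text is also not silent on covariance: it names a within-subject random effect, and a repeated measures model could imply a fuller structure. All of this stands. It makes the concern conditional but does not remove it, because the operative analysis text still does not name the weeks.

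Three stronger inferences are tempting, and the documents do not support them.

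- **That the planned test is known to be inflated.** This needs all weeks, a patient intercept only and positive within-period correlation. The documents fix none of the three, and a week trend can make the test conservative.
- **That a 30% reduction would appear as 22.5% or 25%.** The 30% is a change from baseline, whereas the model estimates liraglutide against placebo. The conversion holds only if placebo changes nothing from baseline. Only the 75% and 83% ratios can be used.
- **That the sample size is wrong.** Its figures reproduce.

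**Conclusion.** The point holds in conditional form and should be fixed. The primary analysis text does not align with the outcome definition and the sample-size section, and its literal reading can give a wrong p-value, which makes this more than a missing detail. On that reading, type I error is about 0.05-0.29 (four weeks) or 0.05-0.37 (six weeks) for assumed shares of 0 to 0.5 without a trend, and as low as 0.012 with one. One mean per period stays at 0.046-0.053.

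The missing specification is certain. The sizes rest on assumed correlations, trends and effect shapes, and the documents do not let a reader say which would apply.

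**What to change.** In DATA ANALYSIS, Primary analyses, state that the primary model uses one 7-day mean per patient per period (week 4 and week 10), with treatment, period and sequence fixed and patient random. Report the treatment difference in BM/day with a 95% CI. The clock restarts at the start of period 2, so week 10 falls four weeks into that period for early and regular crossovers alike. This matches the timing of the primary outcome, not its 30% reduction from baseline.

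State also that period and sequence stay in the model. This replaces the rule that removes non-significant terms, and in effect makes the present sensitivity specification primary.

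Keep any all-weeks model as supportive, with a week term and a patient-by-period random effect. Say that LOCF-filled weeks 5-6 or 11-12 after early crossover or termination are not counted as new observations.

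The cost is wording only: both visits are already scheduled. Power at 1 SD is 0.79 (8 df) against the stated 0.80 (9 df). For shares of 0.3 to 0.5, a correctly specified all-weeks model would have 0.94-0.99 if the effect is constant over weeks, but 0.75-0.945 if it builds up with dose. Making that model primary would also be valid, provided the primary outcome were redefined as an average over weeks.
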